11.1 Extent of Exposure

The extent of exposure to C1-INH in open-label and in double-blind period and to placebo in double-blind period will be summarized using descriptive statistics. Extent of exposure will be described in terms of the following (including intravenous administration and subcutaneous administrations):

- Cumulative administered volume (mL), calculated as sum of single administered volumes in treatment periods,
- Cumulative planned volume (mL), calculated as sum of single planned volumes in treatment periods (planned administration at days 1, 4, 7, 10, and 13 and twice weekly dosing beginning at the day 14 visit in Treatment Period 1 and twice weekly dosing in Treatment Period 2; dosing scheme must be taken into account for cumulative planned dose depending on subjects time in study; the number of administrations in period of twice weekly dosing will be calculated as: $((\text{date of end of twice weekly dosing} - \text{date of start of twice weekly dosing} + 1) / 7) * 2$,
- Days on treatment, calculated as days between first and last dose in treatment periods;
- Average daily dose, calculated as cumulative administered dose divided by days on treatment for each treatment period,
- For subjects continuing C1-INH in Treatment Period 2 cumulative administered dose, cumulative planned dose, days on treatment and average daily dose will be summarized for the whole C1-INH treatment period.

Extent of exposure for Retreatment Periods will be summarized separately.

For summaries of Treatment Period 1 the RiS Analysis Set will be used. Summaries for Treatment Period 2 will be based on the RWS Analysis Set. Also, exposure summary will be presented for the RWS subjects receiving C1-INH during the entire study (Treatment Period 1 and Treatment Period 2 combined).

A by-subject listing will be provided including treatment period (including re-treatment), cumulative administered volume, cumulative planned volume, days on treatment and average daily dose.

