10.20 Treatment Compliance

Percentage compliance will be a function of the amount of IMP taken, ie, the actual cumulative administered volume (mL), and the amount of IMP prescribed, ie, the cumulative planned volume (mL).

Percentage compliance to IMP will be calculated as:

compliance (%) = (cumulative administered volume / cumulative planned volume)*100.

Percentage compliance will be summarized by frequencies of < 80%, 80% – 120%, > 120%.

Percentage compliance will be summarized for the RiS Analysis Set for Treatment Period 1 and by treatment group for the mITT Analysis Set for Treatment Period 2. Percentage compliance will be also summarized for the entire study for the mITT subjects randomized to C1-INH in period 2. Also, compliance will be summarized based on intravenous delivery and subcutaneous delivery of C1-INH during Treatment Period 1.

Subjects may undergo retreatment during the post-treatment Follow-up Period with the blinded investigational product to which they were randomized in Treatment Period 2.

The following listings will be provided:

- Randomized and actual treatments,
- Drug accountability data (dispensed and returned),
- Overall compliance.

A by-subject listing will be provided including compliance by treatment period, by delivery system (intravenous and subcutaneous), randomized and actual treatments.

Calculation of compliance and extend of exposure (see [Section 11.1](#)) will be based on drug accountability data collected by IRT system (or RAVE) as the eCRF does not contain any such related data fields. Drug accountability data will be part of final study data base.

11 Safety Analyses

Open-label safety events and findings will be defined as those with an onset date prior to the randomization date. Double-blind safety events and findings will be defined as those with an onset date on or after the randomization date.

The RiS Analysis Set will be used for analysis of safety for open label TP1. The RWS Analysis Set will be used for analysis of safety during the double-blind period; summaries will be presented by treatment group and total number of subjects in RWS Analysis Set. Also, safety of RWS subjects randomized to C1-INH will be summarized over the study including periods 1 and 2 and follow-up.

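### The SAP's planned-dose formula counts days rather than doses and leaves its end date undefined; if that date is the last dose, regular twice-weekly dosing is undercounted by 0.57 to 0.86 of a dose

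*SAP*

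**What the plan says.** SAP 11.1 (Extent of Exposure) builds the cumulative planned volume from two parts. The five intravenous (IV) doses are counted one by one on Days 1, 4, 7, 10 and 13. For the SC phase, "the number of administrations in period of twice weekly dosing will be calculated as" the inclusive number of days from start to end, divided by 7 and multiplied by 2. No rounding is stated and the end date is not defined. The only guidance is that "dosing scheme must be taken into account for cumulative planned dose depending on subjects time in study". A neighbouring item in the same list does name its limits: "Days on treatment, calculated as days between first and last dose in treatment periods".

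SAP 10.20 (Treatment Compliance) then sets "compliance (%) = (cumulative administered volume / cumulative planned volume)*100". "Percentage compliance will be summarized by frequencies of" below 80%, 80% to 120%, and above 120%. This is done by treatment period, and in addition "compliance will be summarized based on intravenous delivery and subcutaneous delivery of C1-INH during Treatment Period 1".

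**The concern.** The formula credits each dose with 3.5 days of calendar time. If the interval closes on the day of the last dose, that dose is credited with one day, which is 2/7 of a dose. The planned count is then a fraction below the number of doses a fully compliant subject receives, while the IV doses in the same sum are counted whole.

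The shortfall is roughly constant, so it matters little over 51 doses and a great deal over two. A reader of the compliance table would take an entry above 120% as overdosing when no extra dose was given. Near the lower limit, a subject below 80% can be lifted into the middle class.

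**Working it through.** The documents state no planned count for the twice-weekly phase, so there is no figure to reproduce. The formula was applied to ideal schedules.

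**Inputs**
- Interval of 3 or 4 days, ideally on fixed weekdays (Protocol 3.2), so 3- and 4-day gaps alternate.
- TP1 SC phase: Day 14 to the second Week 12 dose (Protocol Table 10). With Week 12 at Day 84, that dose falls on Day 87 or 88.
- TP2: first dose at Week 13 (7 × 13 = Day 91), final dose at the Week 38 visit, Day 266 (Protocol Table 2 and 8.5.4.6).
- Equal volume at each dose, so compliance = doses given / F, where F = ((end − start + 1)/7) × 2.

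**Shortfall when the end is the last dose date**
- Odd number of doses, 2m + 1, last dose at 7m days: F = 2m + 2/7, short by 5/7 = 0.71.
- Even number, 2m + 2, last dose at 7m + 3 days: F = 2m + 8/7, short by 6/7 = 0.86.
- Even number, last dose at 7m + 4 days: F = 2m + 10/7, short by 4/7 = 0.57.

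**Completers**
- TP2: F = (176/7) × 2 = 50.29; 51/50.29 = 101.4%.
- TP1 SC, end Day 87: F = (74/7) × 2 = 21.14; 22/21.14 = 104.1%.
- TP1 SC, end Day 88: F = (75/7) × 2 = 21.43; 22/21.43 = 102.7%.
- TP1, both routes: 27/26.14 = 103.3% or 27/26.43 = 102.2%.

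**Compliant subjects who stop early (TP2, or TP1 SC only)**

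| Doses given | 3-day gap first | 4-day gap first |
|---|---|---|
| 1 | 350% | 350% |
| 2 | 175% | 140% |
| 3 | 131% | 131% |
| 4 | 127% | 116.7% |
| 5 | 116.7% | 116.7% |
| 8 | 112% | 107.7% |

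With shortfall s, k doses exceed 120% only if k < 6s. That allows 1 and 3 (s = 5/7), 2 and 4 (s = 6/7), or 2 (s = 4/7). Over both TP1 routes the five whole IV doses dilute the error: on these schedules the peak is 7/6.14 = 114%.

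**Lower class limit.** 17 of 22 SC doses is 77.3%. With the last dose on Day 87 it reads 17/21.14 = 80.4% and changes class. With Day 88 it reads 17/21.43 = 79.3% and does not.

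**Other end dates and conventions**
- TP1 SC, end Day 90 (the day before the first TP2 dose): (77/7) × 2 = 22.0, exactly 100%.
- TP1 SC, end Day 91: 22.29 planned, 98.7%.
- Two doses three days apart, end date 7 days after the second: (11/7) × 2 = 3.14 planned, 63.6%, in the class below 80%.
- All gaps of 4 days, 22 doses: F = (85/7) × 2 = 24.29, 90.6%.
- Planned volume left unrounded, 70 kg TP2 completer: (51 × 8)/(50.29 × 8.4) = 96.6%.

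**The case against.** A reader might infer that perfect compliance always reads above 100% and that compliant early stoppers in general are classed above 120%. The documents do not support either statement. The end date is undefined, and the SAP's reference to time in study, beside an item that names first and last dose explicitly, leaves room for a later date. On such a date the formula can be exact or can overcount. Repeated 4-day gaps, which the dosing text allows, also bring the result below 100%. So can planned volume, if it is not rounded down to whole mL as the administered volume is (Protocol 6.1.3.1); SAP 11.1 does not say. Even on the last-dose reading, only stops within about the first ten days of SC dosing exceed 120% on the regular schedule.

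All of this stands as a limit on the claim. It does not remove it. For TP2 the last-dose reading is the natural one: the period opens and closes with a dose, and no TP2 dose is due after Week 38. SAP 8.2.9 likewise ends a Retreatment Period at the last intake of study drug. An end date that decides whether the same two doses read 175% or 63.6% has to be written down.

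It is also fair that little depends on these tables. Compliance defines no analysis set, no hypothesis is tested after early termination, the formula is the same in both arms, and the by-subject exposure listing shows administered and planned volume.

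**Conclusion.** The formula needs correcting, as a minor point. On a regular 3/4-day alternation with the end taken as the last dose date, planned SC administrations are short by 0.57 to 0.86 of a dose. Full compliance is overstated by 1.4 percentage points for TP2 completers and by 2.7 to 4.1 points for TP1 SC, with no change of class. Subjects who stop after one to three SC doses, or four on a 3-4-3 pattern, are classed above 120% in TP2 or in the SC-only TP1 summary. TP1 compliance over both routes does not exceed 120%.

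These figures assume equal volumes per dose and planned volume rounded as administered. With 13 subjects randomized (SAP 3), one misclassified TP2 subject is at least 1/13 = 7.7% of those tabulated. The effect stops at descriptive compliance and exposure summaries.

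**What to change.** In SAP 11.1:
1. Define start and end as the dates of the first and last dose of the twice-weekly phase in each period.
2. Set planned administrations to round((last − first)/3.5) + 1, or round the existing formula up to a whole number. On either 3/4-day alternation both return 22 for TP1 SC, 51 for TP2, and the exact count for early stops.
3. Calculate planned volume with the same rounding down to whole mL as the administered volume.

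The first step is essential. Applied to an end date of Day 90 or 91, the new expression gives 23 planned doses for 22 scheduled. The SAP should also say that compliance so defined runs to the last dose, so doses omitted after it are not counted as missed.

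The cost is one formula and two short definitions, with no new data.

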4.3 Study Treatments

Dose and Dosing Regimen

A summary of dose and dosing regimen is shown in Table 4.

Table 4 Summary of dose and dosing regime

Timeframe	Intravenous Administration	Subcutaneous Administration
Treatment Period 1: The Day 1 Visit to the Day 13 Visit ^a	60 IU/kg C1-INH	Not applicable
Treatment Period 1: The Day 14 Visit to the Week 12 2 nd Visit ^a	Not Applicable	60 IU/kg C1-INH
Treatment Period 2: Week 13 to the Week 38 Visit ^b	Not Applicable	60 IU/kg C1-INH OR 0.12 mL/kg Placebo
Re-treatment Period: The Retreatment Day 1 Visit to the Retreatment Week 26 Visit. ^c	Not Applicable	60 IU/kg C1-INH OR 0.12 mL/kg Placebo

IV = intravenous; SC = subcutaneous

^a Treatment Period 1 is open-label and each subject will receive C1-INH. C1-INH (60 IU/kg) will be administered IV to each subject over the first 13 days of Treatment Period 1 for a total of 5 doses. Thereafter, C1-INH (60 IU/kg twice weekly) will be administered SC to each subjects for the remainder of Treatment Period 1. The first dose of randomized investigational product will be administered to responders at the Week 13 Visit.

^b Treatment Period 2 is blinded and subjects will be randomized 1:1 to treatment with investigational product (C1-INH [60 IU/kg] or placebo) subcutaneously twice weekly.

^c Retreatment Period(s) are blinded and subjects will receive the same investigational product treatment assignment as received during Treatment Period 2.

Note: Week 13 is the final visit of Treatment Period 1 for non-responders and the first visit of Treatment Period 2 for responders.

Treatment Period 1

C1-INH will be administered to all subjects during Treatment Period 1 in an open-label manner. Five doses of C1-INH will be administered intravenously to subjects at the Day 1, 4, 7, 10, and 13 Visits. Intravenous C1-INH will be administered at the study site during site visits. Subcutaneous C1-INH will be administered every 3 to 4 days (ie, twice weekly) beginning at the Day 14 Visit and for the remainder of Treatment Period 1. Subcutaneous C1-INH is required to be administered at the study site during site visits, but at other times may instead be administered at home by a medical professional ((eg, a home visit nurse) or by the subject under the supervision of a medical professional.

Treatment Period 2

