Subcutaneous administration of the investigational product should be via a single SC injection in the abdomen, thigh, upper arm, or other appropriate location. The twice weekly administration of investigational product beginning at the Day 14 Visit and during any Retreatment Period (if applicable). The suggested interval between each administration of investigational product is 3 or 4 days (ie, twice weekly). In addition, the investigational product should ideally be administered at approximately the same time on each day. A missed injection should be administered as soon as possible, unless within 24 hours of the next scheduled injection; in this situation, the missed injection should be omitted, and the administration of investigational product should occur at the next scheduled day and time. The volume of investigational product to be administered will be based on each subject's body weight (from the Screening physical examination) and will not be adjusted during the study.

Description of Investigational Products

The investigational products for this study are C1-INH and placebo. A description of C1-INH and Placebo and given in Table 5 and [Table 6](#) respectively.

Table 5 Description of C1-INH

Substance name	C1-esterase Inhibitor, Human (500 IU/mL)
Active substance	C1-esterase inhibitor (human)
Trade name	Not applicable
Dosage form	Lyophilized powder for reconstitution; 1500 IU C1-INH per single-use vial.
Dose	60 IU/kg
Mode of administration	Intravenous / subcutaneous injection

Before use, each vial of C1-INH is reconstituted with 3 mL water for injection. 60 IU/kg C1-INH is equivalent to a volume of 0.12 mL/kg.

Table 6 Description of Placebo

Substance number	Not applicable
Substance	Excipients of C1-INH plus albumin
Trade name	Not applicable
Dosage form	Lyophilized powder for reconstitution
Dose	0.12 mL/kg
Mode of administration	Subcutaneous injection

Before use, each vial of placebo is reconstituted with 3 mL water for injection.

The volume of placebo will be based on the body weight obtained with vital signs assessment at the Screening Visit, and will not be changed through the study. The actual dose of placebo will be rounded to the lowest 1 mL as if the subject receiving C1-INH.

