8.2.2 Study Day for Safety Measures

If the date of interest occurs on or after the safety reference date, then the safety study day will be calculated as (date of interest - safety reference date) + 1. If the date of interest occurs before the safety reference date, then the safety study day will be calculated as (date of interest – safety reference date). There is no safety study day 0.

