8.2.4 Durations

Durations (eg, the duration of an adverse event) and elapsed time will be calculated in days using the SAS DATDIF function.

When reporting durations which are calculated in months, divide the number of days by 30.4375; to report in weeks divide the number of days by 7; to report in years divide the number of days by 365.25. These algorithms for time to event return decimal numbers, and ignore the actual numbers of days in the months or years between start date and stop date. The "year" used in these algorithms is 365.25 days long, and the "month" is one twelfth of that year.

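### Days on treatment in SAP 11.1 is one day short of an inclusive count, so average daily dose is undefined after a single dose and too high otherwise (wrong as written, minor)

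*SAP*

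**What the plan says.** SAP 11.1 (Extent of Exposure) defines two linked variables: "Days on treatment, calculated as days between first and last dose in treatment periods", and "Average daily dose, calculated as cumulative administered dose divided by days on treatment for each treatment period". It gives no rule for a subject with a single dose.

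The general rule in SAP 8.2.4 is "Durations (eg, the duration of an adverse event) and elapsed time will be calculated in days using the SAS DATDIF function". That is a date difference, and no day is added.

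Elsewhere the SAP adds the day explicitly when it wants both end dates counted. In SAP 8.2.2, for dates on or after the reference date, "then the safety study day will be calculated as (date of interest - safety reference date) + 1". In SAP 11.1 itself, the planned number of twice-weekly administrations is end date minus start date plus 1, divided by 7 and multiplied by 2.

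Both variables are to be summarised for TP1 (RiS set) and TP2 (RWS set), and for the whole C1-INH period in subjects who continue C1-INH. Retreatment exposure is summarised separately. A by-subject listing is also planned. Under SAP 6.5, one dose in the relevant period is enough to enter either safety set.

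**The concern.** The numerator includes the dose given on the first day, but the denominator does not count that day. With one dose the denominator is zero. With a few doses, one missing day is a large share of the total; with a full course it is negligible.

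Two outputs are affected. Days on treatment reads 0 for a subject who was dosed, and one day low for everyone else. Average daily dose is missing for one-dose subjects and too high for the rest, most of all for those who stop early. The SAP also counts days in two ways within one section: planned volume inclusively, days on treatment not.

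**Working it through.** The documents state no average daily dose, so there is no figure to reproduce.

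**Inputs**
- Dose per administration: 60 IU/kg ("60 IU/kg C1-INH is equivalent to a volume of 0.12 mL/kg", SAP 4.3; consistent, since 60 / 500 IU/mL = 0.12 mL/kg).
- IV schedule: "Five doses of C1-INH will be administered intravenously to subjects at the Day 1, 4, 7, 10, and 13 Visits" (SAP 4.3).
- TP1 SC schedule: twice weekly from Day 14 to the second Week 12 dose (Protocol Table 10). At nominal days this is 11 weeks × 2 = 22 doses, the last on Day 87 or 88. With 5 IV doses, a TP1 completer has 27.
- TP2: first dose at Week 13 (13 × 7 = Day 91), last at Week 38 (Day 266, Protocol Table 2). Twice weekly with a dose on both end days gives 51 doses.

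**Formulas.** Let n be the number of doses and t = last dose date − first dose date.
- As written: 60n / t
- Inclusive count: 60n / (t + 1)
- Ratio of the two: (t + 1) / t

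The ratio does not depend on dose, body weight or unit. That matters because SAP 11.1 gives volumes in mL and names no unit for average daily dose.

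**Results (IU/kg/day)**

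| Course | n | t | As written | Inclusive | Excess |
|---|---|---|---|---|---|
| One dose | 1 | 0 | 60/0, undefined | 60/1 = 60 | – |
| Two IV doses | 2 | 3 | 120/3 = 40 | 120/4 = 30 | 33% |
| Three IV doses | 3 | 6 | 180/6 = 30 | 180/7 = 25.7 | 17% |
| Five IV doses | 5 | 12 | 300/12 = 25 | 300/13 = 23.1 | 8% |
| TP1 completer, last dose Day 87 | 27 | 86 | 1620/86 = 18.8 | 1620/87 = 18.6 | 1.2% |
| TP1 completer, last dose Day 88 | 27 | 87 | 1620/87 = 18.6 | 1620/88 = 18.4 | 1.1% |
| TP2 completer | 51 | 175 | 3060/175 = 17.49 | 3060/176 = 17.39 | 0.6% |
| TP1 + TP2 on C1-INH | 78 | 265 | 4680/265 = 17.66 | 4680/266 = 17.59 | 0.4% |

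**Sensitivity.** The ±1 day visit windows and the 48-hour minimum between IV doses (Protocol Table 1 and footnotes) allow 2 to 5 days between the first two IV doses. The excess after two IV doses then runs from 3/2 − 1 = 50% down to 6/5 − 1 = 20%. For two SC doses 3 or 4 days apart it is 33% or 25%.

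**The case against.** The strongest case against is that very little depends on this variable. Compliance, which is where dosing is judged against plan, is administered volume over planned volume and is already split by IV and SC in TP1 (SAP 10.20); it does not use days on treatment. Adverse event tables count subjects, not events per unit of exposure (SAP 11.2). The exposure listing shows volumes and days beside average daily dose, and continuous summaries report the number of observations (SAP 7), so a 0-day or undefined value would be visible. Thirteen subjects were randomised before termination (SAP 3), no hypothesis is tested (SAP 4.2.1.3, 7.3), and the documents do not say whether any subject stopped after one or two doses. All of this stands, and it sets the severity. It does not make the written rule right.

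Three stronger readings are tempting, and the documents do not support them.

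- A reader might infer that average daily dose is doubled after two IV doses, because 40 is twice 60/3 = 20. That compares it with the scheduled rate, as if each dose covered the interval after it. The SAP sets no such target. Against an ordinary inclusive count the excess is 33%.
- A reader might infer that the TP1 table would show dosing above anything the protocol delivers. The protocol allows IV doses 48 hours apart (60/2 = 30 IU/kg/day over that interval) and places the first SC dose 24 to 48 hours after the last IV dose (60 to 30). Doses are also rounded down to a whole mL (Protocol 5.1.1). For an assumed 70 kg subject, 8.4 mL becomes 8 mL, or 8 × 500 / 70 = 57.1 IU/kg. The as-written TP2 completer value is then 51 × 57.1 / 175 = 16.7, below the nominal 120/7 = 17.1.
- A reader might infer that early stoppers are lost to the tolerability assessment. They remain in the RiS set, the disposition table (SAP 9.1) and, where an adverse event led to stopping, the discontinuation listings (SAP 11.5).

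**Conclusion.** Wrong as written, minor. The definition gives 0 days and an undefined average daily dose for a single-dose subject, and a denominator one day short for everyone else. The size depends on course length: 33% after two IV doses, 8% after five, about 1% for a TP1 completer and 0.6% for a TP2 completer. For a subject with two or more doses, the overstatement is relative to that subject's own inclusive count; someone who misses doses may still fall below the scheduled rate.

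The figures assume nominal visit days, the full 60 IU/kg at each dose, and SAP 11.1 and 8.2.4 read literally. If the sponsor meant an inclusive count, the text still needs the change, because the SAP states the added day elsewhere and a programmer following SAP 11.1 would leave it out. Efficacy, compliance and adverse event results are unaffected. With so few subjects, one early stopper could visibly shift a mean or set a maximum, but whether any such subject exists is not stated.

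**What to change.** In SAP 11.1, define days on treatment as last dose date − first dose date + 1 within each treatment period. Apply the same rule to the combined C1-INH summary and the retreatment summaries, and use the result as the denominator of average daily dose.

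Add a table footnote that values after one or two doses are not comparable with the scheduled rate. The added day removes the zero division but still gives 60 IU/kg/day after one dose and 30 after two IV doses, against 20 for one dose every 3 days.

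Extending the denominator by the scheduled interval after the last dose would be an alternative, but it is a preference and not needed to correct the error. For an IV-only figure it would need its own transition rule: last − first + 3 gives 12 + 3 = 15 days (Days 1 to 15), overlapping the SC dosing that starts on Day 14.

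The cost is one line of SAP text, one line of programming and a footnote. No data change is needed.
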